### 7.2.4 Death

Participants who die while on study will be replaced by another new patient.

### 8.0 DATA MANAGEMENT

### 8.1 Case Report Form Set

The CRF, a set of forms for each participant, provides a record of data generated according to protocol. These forms are to be completed on an ongoing basis during the study. The research chart is the source of verification of data. During the study, CRFs will be monitored for completeness, accuracy, legibility and attention to detail. The CRFs will be retained for review.

### 8.2 Data Entry, Data Management and Quality Control

Hard copies of the data are kept in folders in the project coordinators' office, where it will be available for the project coordinators to evaluate whenever overall protocol assessment is wanted or needed. The coded list of participants on the study is maintained in a locked cabinet by the PIs. Confidentiality will be maintained and information kept on each participant will be made available only to the project coordinator and identified investigators.

### 8.3 Additional Reporting Requirements

### 8.3.1 Protocol revisions and amendments

- The IRBMED must be notified of proposed protocol amendments to assess impact on trial safety and management of regulatory submission.
- A full copy of the amended protocol must be submitted to the IRBMED for review and approval prior to initiating the amended protocol.
- The revised or amended protocol document must be accompanied by a cover sheet detailing the protocol changes, rationale for change, impact on other areas of the protocol, and specific reference to the changed protocol sections.
- The protocol shall be clearly marked with the protocol version number or amendment number
- All protocol amendments must be approved by the IRBMED prior to activation.

### 9.0 STATISTICAL METHODS

Baseline sociodemographic and clinical characteristics will be analyzed by treatment groups, using means and standard deviations (SD), counts and percentages as appropriate. Comparisons between groups on baseline characteristics will be tested using an independent sample t-test for continuous measures or Pearson's Chi-square, for categorical variables. In all analyses, a p-value of  $\leq$  0.05 was considered statistically significant. All tests will be two-sided.

## 9.1 Primary and Secondary Aims

To investigate the change through time both within and between groups for fatigue (BFI), we will use linear mixed models (LMM). An advantage of LMM is that it acts as essentially an intent-to-treat (ITT) analysis as it uses all available data at each time point. For each LMM, a random subject intercept will be included to account for subject clustering; visit, group, and the interaction term (visit by group), will also be included as fixed effects. The models for BFI will be controlled for the fixed effects of any baseline variable such as age or lupus disease activity that is significantly different at baseline. Normality of the residuals derived from the LMM will be assessed using the Shapiro–Wilk test and q-q plots. For non-normal results a Box-Cox transformation will be utilized. The same methods will be employed to investigate secondary outcomes of interest pain (BPI severity sub-scale), sleep (PSQI global score) and quality of life (RAND SF-36).

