### 4.0 METHODS

We propose to perform a randomized, single-blind parallel clinical trial. This will be parallel design with four arms (relaxing acupressure plus usual care, stimulating acupressure plus usual care, sham acupressure plus usual care and usual care alone) for persistent fatigue in SLE. The study will be approximately 12 weeks in duration: **Screening** (up to 30 days in duration) consists of a phone call evaluation for study eligibility; **Treatment** (active treatment phase; 6 weeks in duration) will consist of random assignment to self-administered acupressure regiment plus usual care or usual care only daily for 6 weeks (outcomes will include fatigue, sleep, QOL, pain); and **Post-treatment follow-up** (4 weeks in duration) to evaluate the persistence of effects following 4 weeks of no treatment. We will allow up to +/- 2 weeks difference for study visits and the interim phone call in order to accommodate schedules.

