# Table 2.0 Eligibility Criteria

Inclusion Criteria		Exclusion Criteria		
✓ ✓ ✓	Women aged 18 years and older Report chronic (>3months) clinically relevant fatigue, defined as a score of ≥4 on the Brief Fatigue Inventory (BFI) Have inactive disease, defined as SELENA SLEDAI ≤ 4, AND/OR no addition or increase in dose of corticosteroids, immunosuppressive agents, or	* *	Pregnant or breast feeding Have a diagnosis of untreated mood disorder, e.g., bipolar or major depressive disorder Have an initiation, a cessation or change of treatment of any chronic medications, dietary supplements, behavioral therapy, physical therapy etc., or any planned change of medications, supplements or therapies during the study	
✓	antimalarial medications or hospitalization in the last 30 days Have no commonly recognized medical explanations for fatigue (a history of cancer in the previous 5 years –except for certain low risk cancer, unstable thyroid disease, moderate to severe chronic kidney disease, moderate to severe anemia)	×	Acupuncture or acupressure receipt in past year	
√ √	Baseline glucocorticoid dose equivalent of ≤10mg prednisone. No other planned intervention for fatigue other than current stable medication regimen			

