### 4.7 Study Visits

#### 4.7.1 Screening- Participant Interaction #0 (to determine eligibility)

A screening phone call will be made to evaluate participant interest and eligibility including, comorbidities and ability to maintain a stable lifestyle over the course of the study. Sociodemographic and participant contact information will be collected. Fatigue will be assessed using the Brief Fatigue Inventory (BFI) and baseline depression and lupus disease activity status with the Patient Health Questionnaire 9 (PHQ-9) and the Systemic Lupus Activity Questionnaire (SLAQ). If a potential participant is not a part of the U of M health system they will complete the Connective Tissue Screening Questionnaire (CSQ) and will be sent an Authorization for Release of Protected Health Information form to complete and give to their health care provider.

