### 4.7.2 Randomization/Baseline- Participant Interaction #1 (Week 0, +/- 2 weeks)

Written informed consent will be obtained at the beginning of the study visit. Medication and health history, concomitant medications, lupus disease activity and urine pregnancy test results will be collected if applicable. Participants will complete BFI, SLAQ, PROMIS Fatigue Short Form 8 (PROMIS Fatigue 8), RAND SF-36, Pittsburg Sleep Quality Index (PSQI), the Brief Pain Inventory (BPI), Generalized Anxiety Disorder 7 (GAD7), The Satisfaction With Life Scale (SWLS), Fibromyalgia Survey Criteria (FM Survey Criteria), International Physical Activity Questionnaire (IPAQ) and The Positive and Negative Affect Schedule (PANAS). Participants will be instructed in how to perform their acupressure and told to start their acupressure on the following day. Participants will complete the Acupressure Fidelity test after the acupressure instruction has been completed. A study logbook will be dispensed, to document conduct of acupressure and the time of day. The post-treatment visit will be scheduled for exactly six weeks from the start day and the follow-up visit for four weeks post termination of treatment.

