### 9.2 Sample Size Justification

Power is computed via simulation using LMM with a group, week, group by week interaction, and a random subject effect. Mean BFI values at week 6 are taken to be 4, 3, 2 at the end-treatment point for usual care, stimulating acupressure, and relaxing acupressure. The between-subject variance is assumed to be 4 at all time-points; whereas the variance of the random subject component was also 4 with an intra-class correlation of 0.5. For this configuration, power for detecting group differences is > 0.80 and power for detecting a significant week by group interaction is 0.62 with a sample size of 15 per treatment arm and 5% level of

significance. We assume a 16 to 17% drop-out rate based on previous studies and thus plan to recruit 18 per arm to ensure that 15 participants complete the entire 10-weeks of the study.

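### BFI is taken twice before treatment, but section 9.1 does not use the screening score; a baseline-adjusted model that did would estimate the week-6 contrast with about 5% to 8% less variance

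*Combined protocol and SAP*

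**What the plan says.** Section 4.7.1 takes a BFI at the screening phone call: "Fatigue will be assessed using the Brief Fatigue Inventory (BFI". Section 4.7.2 takes a second one at the randomisation/baseline visit, with acupressure starting the next day: "Participants will complete BFI, SLAQ, PROMIS Fatigue Short Form 8 (PROMIS Fatigue 8), RAND SF-36". The schedule in section 4.6 marks both. Screening is described in section 4.0 as "up to 30 days in duration". Table 2.0 requires clinically relevant fatigue, "defined as a score of ≥4 on the Brief Fatigue Inventory (BFI", so the score used for entry is cut off from below.

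For the analysis, section 9.1 says that "a random subject intercept will be included to account for subject clustering" and that "visit, group, and the interaction term (visit by group), will also be included as fixed effects". It does not say which interactions count as visits. A baseline variable enters the BFI model only if the arms differ significantly on it. Neither pre-treatment BFI score is named as a covariate, and no section gives the screening BFI an analytic role beyond eligibility.

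Section 9.2 gives the only information on correlation: "the variance of the random subject component was also 4 with an intra-class correlation of 0.5".

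**The concern.** With an intra-class correlation of 0.5, half the variance of a single BFI reading is within-person. One baseline reading is therefore a noisy measure of a woman's usual fatigue, and a second pre-treatment reading adds information that the first does not hold. The trial expects only about 15 completers per arm, so every contrast in Aim 2 will be imprecise, and the second reading costs nothing to collect.

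What is at stake is a small amount of precision on the primary measure. There is also a specification gap: the set of outcome visits and the role of pre-treatment BFI are left open, and it is better to settle both before the data are seen.

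**Working it through.** **Inputs from the documents.** Intra-class correlation r = 0.5; total variance 4 or 8 (the wording of 9.2 allows either); entry cut BFI ≥ 4; 15 completers per arm, four arms, 60 in all.

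**Assumptions not in the documents.** Normal scores; the cut applied to the screening score; a pre-selection BFI mean of 4.5 to 6.5; equal correlation between every pair of BFI scores, as a random-intercept model implies.

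**The plan's own figure.** 15/(1 − 0.16) = 17.9 and 15/(1 − 0.17) = 18.1, so 18 per arm reproduces. The stated power cannot be checked in full, because 9.2 gives no sham, baseline, week-2 or week-10 mean. Nothing below depends on it.

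**Step 1: the model as written.** Take the variance of a two-arm week-6 contrast as a multiple of 2σ²/n. With a free mean for each arm at each visit, it is 1.00. Change from baseline has multiple 2(1 − r) = 1.00 as well. Adding screening as one more visit leaves both at 1.00.

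**Step 2: pre-treatment scores as covariates, ignoring the cut at 4.**
- Baseline only: 1 − r² = 0.75.
- Baseline and screening: 1 − 2r²/(1 + r) = 1 − 0.5/1.5 = 0.667.
- Further cut: 1 − 0.667/0.75 = 11.1%.

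**Step 3: with the cut at 4.** Let k be the variance of the truncated screening score divided by σ². Among women who enter, the variance of baseline (and of untreated week 6) is V = 0.25k + 0.75 and their covariance is C = 0.25k + 0.25, both in units of σ². The residual variance given baseline alone is V − C²/V. Given both scores it stays at 0.667, because selecting on a predictor does not alter the residual variance.

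Example: mean 5.5, SD 2. The cut lies 0.75 SD below the mean, and k = 0.556. Then V = 0.889 and C = 0.389. The residual is 0.889 − 0.151/0.889 = 0.719, and the cut is 1 − 0.667/0.719 = 7.3%.

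| Pre-selection mean | Total variance 4 | Total variance 8 |
|---|---|---|
| 4.5 | 5.8% | 5.6% |
| 5.5 | 7.3% | 6.6% |
| 6.5 | 8.7% | 7.6% |

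Simulation agrees with these large-sample figures. The two scores have equal coefficients here, r/(1 + r) = 1/3 each, so their average gives up none of the gain and adds no covariate beyond the one that baseline would use.

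**Step 4: cost of a separate covariate.** With 60 completers in four arms, moving from one covariate to two inflates the contrast variance by (1 + 2/53)/(1 + 1/54) = 1.019. The net cut runs from 1 − 0.944 × 1.019 = 3.8% to 1 − 0.913 × 1.019 = 7.0%. Direct simulation at 15 per arm and total variance 4 gave 3.5%, 5.7% and 6.6% for means 4.5, 5.5 and 6.5.

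**Step 5: baseline left as an outcome visit.** The target is then week 6 minus baseline. Its covariance with screening is rσ² − rσ² = 0. Its variance is 2(1 − r)σ², which is 4.00 with or without the screening covariate at σ² = 4, and 8.0 with or without it at σ² = 8. The gain is nil.

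**Step 6: what the gain is worth.** A cut of 5% to 8% equals 15/0.95 = 15.8 to 15/0.92 = 16.3 completers per arm, or about one more per arm. Confidence intervals narrow by 1 − √0.95 = 2.5% to 1 − √0.92 = 4.1%. For a 2-point pairwise difference, a 6% cut from the 0.75 multiple raises power from 0.885 to 0.903 (SD 2) or from 0.609 to 0.635 (SD 2.83).

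**Step 7: sensitivity.**
- With the cut at 4 and means of 5 to 7, the large-sample gain is about 4–7% at a correlation of 0.4, 8–12% at 0.6 and 11–15% at 0.7.
- If screening correlates with week 6 at 0.40 rather than 0.50, the gain without truncation falls from 11.1% to 4.0% (screening–baseline correlation 0.5) or 2.1% (correlation 0.6).

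**The case against.** The strongest reply is that 9.1 contains no baseline-adjusted model, so the gain is measured against a model the plan does not have. That stands. Using baseline BFI properly is the larger step (1.00 to 0.75), and the screening gain comes only on top of it. A reader might infer that adding the screening score helps however baseline BFI is handled. Step 5 shows that it does not.

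A second reply is that the size rests on thin assumptions: an invented pre-selection mean, a correlation taken from a cited study that is not among the documents, and a phone score up to 30 days old assumed to predict week 6 as well as the baseline visit does. This also stands, and it is why the result is given as a range. Equal correlation is, however, what the plan's own random-intercept model implies.

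A third reply is that leaving a screening value out of the model is common and valid, especially in a pilot with exploratory efficacy aims. I agree that no invalid inference follows.

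A reader might also infer that the model wrongly treats a truncated screening score as an outcome. The documents do not support that. Section 4.7.1 presents the call as an eligibility step, and the schedule puts Interaction #0 under screening and labels Interaction #1 as baseline. Even if screening were counted as a visit, the week-6 contrast variance would stay at 1.00, and no bias in it has been shown. Such a reading would only add 3 pre-randomisation degrees of freedom to the visit-by-group test, from 3 × 3 = 9 to 3 × 4 = 12, and bring regression to the mean into within-arm change measured from screening. Listing the outcome visits removes the ambiguity.

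**Conclusion.** The point holds as a modest, nearly free gain in precision. Two pre-treatment BFI scores exist and 9.1 makes no effective use of the first. In a model that already adjusts for baseline BFI, using both lowers the week-6 contrast variance by about 5% to 8% when they are averaged (8.7% in the most favourable setting tried), or by about 3.5% to 6.5% net when screening is a separate covariate at 15 per arm.

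This rests on an intra-class correlation of 0.5, equal correlations over time, the entry cut of 4 acting on the screening score, and an assumed pre-selection mean of 4.5 to 6.5. It is conditional on baseline BFI being a covariate, or on pre-treatment means being held equal across arms. It should not be read as bias, as an error in the model, or as the whole loss from the current specification.

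**What to change.** In section 9.1, state in advance that the BFI outcome visits are weeks 2, 6 and 10 only. State also that the mean of the screening and baseline BFI enters as a fixed covariate together with its interaction with visit. Entering both scores separately is acceptable but keeps less of the gain at this sample size. The change should be made together with the adoption of baseline BFI as a covariate; added to the present model on its own, it would not improve the change-from-baseline contrast.

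The cost is a sentence or two in the plan and at most one or a few degrees of freedom. The screening call comes before written consent, which section 4.7.2 places at the start of the baseline visit, so the team should confirm that the consent form covers research use of the screening score. The consent pages are not among the documents reviewed, so it may already do so.

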# 4.3 Randomization and Stratification.

Our randomization scheme will be created by our study statistician. Eligible patients will be randomized into one of four groups: once daily relaxing acupressure, once daily stimulating acupressure, once daily sham acupressure or usual care in a 1:1:1:1 ratio for a total of 72 participants with 18 randomized into each group.

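### BFI covariates are chosen by baseline significance tests and baseline means are left free in each arm; a pre-specified baseline-efficient model would cut week-6 contrast variance by roughly 10–25% with data already collected

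*Combined protocol and SAP*

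**What the plan says.** Section 9.1 fits a linear mixed model to BFI with a random subject intercept, and states that "visit, group, and the interaction term (visit by group), will also be included as fixed effects". It then controls the model for "any baseline variable such as age or lupus disease activity that is significantly different at baseline". The same methods apply to pain (BPI), sleep (PSQI) and quality of life (RAND SF-36).

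Section 9.0 says how the baseline differences are found: they "will be tested using an independent sample t-test for continuous measures", with Pearson's chi-square for categorical ones, at the 5% level. It names a class of variables (sociodemographic and clinical) but no list. Section 4.3 has four arms: "Eligible patients will be randomized into one of four groups". The plan does not say which pairs the t-test compares.

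Nothing in sections 9.0 to 9.2 pre-specifies baseline BFI as a covariate or sets a common baseline mean. BFI is scheduled at screening and at weeks 0, 2, 6 and 10 (section 4.6).

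**The concern.** There are two faults, and they differ in weight.

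1. **The selection rule.** After randomisation, baseline differences between arms are chance. A rule that adjusts for whatever reaches p ≤ 0.05 picks covariates by accident of allocation, not by whether they predict fatigue. The BFI model therefore cannot be written down in advance. The screening test is also not defined for four arms.

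2. **Use of baseline BFI.** With visit, group and their interaction all free, baseline BFI enters as a week-0 response whose mean is estimated separately in each arm. The arms have equal expected baselines by design, and the model does not use that fact.

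What is at stake is precision and a fixed model, not bias or type I error. In a 72-person pilot with 15 completers per arm, precision is scarce.

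**Working it through.** **Inputs.** Section 9.2 gives 15 completers per arm, ICC 0.5, 5% level and week-6 means of 4 (usual care), 3 (stimulating) and 2 (relaxing). Its variance wording is unclear: "whereas the variance of the random subject component was also 4 with an intra-class correlation of 0.5". The total variance σ² may be 4, or 8 (subject 4 plus residual 4), so both are shown. The percentage savings in steps 1 to 3 and 5 depend only on the ICC. In step 4 σ² also enters, through the truncation point.

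**The plan's own figures.** 15/(1 − 1/6) = 18 per arm and 4 × 18 = 72 both reproduce. The stated power (above 0.80 for group, 0.62 for interaction) could not be reproduced jointly, because no sham mean, baseline mean or visit profile is given. That is a separate matter; nothing below relies on it.

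**1. Week-6 contrast between two arms, no truncation** (n = 15, ρ = 0.5, σ² = 4)
- Raw week-6 difference: 2σ²/n = 8/15 = 0.533
- Difference in change: 4σ²(1 − ρ)/n = 8/15 = 0.533
- Baseline-efficient: 2σ²(1 − ρ²)/n = 6/15 = 0.400

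The saving is 1 − 0.400/0.533 = 25% against either contrast. Estimating the slope from 60 completers in four arms multiplies the variance by 1 + 1/54 = 1.0185. The saving is then 1 − 0.75 × 1.0185 = 23.6%; simulation gave 23.3% and 23.6%.

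**2. 18 recruited, 15 completing.** Section 9.2 says "plan to recruit 18 per arm to ensure that 15 participants complete the entire 10-weeks of the study". If the three lost per arm have baseline only, the planned model already uses those baselines. Its change contrast has variance 2[σ²(1 − ρ²)/15 + (1 − ρ)²σ²/18] = 2(0.200 + 0.0556) = 0.511. The saving is 1 − 0.400/0.511 = 22%.

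**3. Against the plan's own rule applied to baseline BFI, week-6 difference reported** (simulation, 200,000 runs). Six pairwise t-tests flag baseline BFI 20.4% of the time and leave a variance of 0.478. One four-group test flags it 4.9% of the time and leaves 0.513. Always adjusting gives 0.407. The savings are 15% and 21%.

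**4. Entry rule truncates the baseline score itself.** Table 2.0 requires BFI of at least 4. Let k be the fraction of baseline variance left after truncation. At ρ = 0.5 the raw and change variances are both (2σ²/15)(0.75 + 0.25k), against (2σ²/15)(0.75) for the efficient model. For σ² = 4:

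| Assumed untruncated mean | k | Planned variance | Saving | After slope |
|---|---|---|---|---|
| 4 | 0.363 | 0.448 | 10.8% | 9.2% |
| 5 | 0.486 | 0.465 | 13.9% | 12.4% |
| 6 | 0.630 | 0.484 | 17.3% | 15.8% |
| 7 | 0.773 | 0.503 | 20.5% | 19.0% |

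At σ² = 8 the saving with slope known is 10.8–17.8%.

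**5. Entry rule acts on the screening call, baseline measured again.** Section 4.7.1 says "A screening phone call will be made to evaluate participant interest and eligibility" and scores BFI on that call; section 4.7.2 measures it again. With the same k, the baseline to week-6 correlation becomes r = [0.5 − 0.25(1 − k)]/[1 − 0.25(1 − k)], which at σ² = 4 is 0.405 at mean 4 and 0.470 at mean 7. After slope estimation the saving against change is 1 − 1.0185(1 + r)/2 = 28% to 25%. Against the raw difference it is 1 − 1.0185(1 − r²) = 15% to 21%.

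**6. Other correlations (assumed), no truncation, slope known.** Against change the saving is (1 − ρ)/2: 35% at 0.3 and 15% at 0.7. Against the raw difference it is ρ²: 9% and 49%.

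**7. Power** (noncentral t, 56 df before and 55 after, slope cost included)

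| Contrast | σ² = 4 | σ² = 8 |
|---|---|---|
| 2 points (relaxing v usual care) | 0.77 to 0.87 | 0.48 to 0.59 |
| 1 point | 0.27 to 0.34 | 0.16 to 0.19 |

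For the 2-point contrast, step 2 gives 0.79 to 0.87 and 0.49 to 0.59 (slope known). Step 4 starts from 0.79–0.84 and 0.51–0.55 and ends at the same 0.87 and 0.59.

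**8. The selection rule alone.** A null continuous variable is flagged about 20% of the time with six pairwise t-tests and 5% with one four-group test. Suppose one flagged covariate explains an assumed 25% (10–50%) of between-subject variance, with 18 per arm and σ² = 4. Adjusting then moves the raw week-6 difference by about 0.31 (0.20–0.43) points, averaged over the six arm pairs, and by about 0.53 for the flagged pair at 25%. The change contrast moves by 0 with complete data, because a covariate entered only as a main effect cancels, and by 0.02–0.05 with one-sixth dropout.

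**The case against.** The strongest reply is that the percentage does not come from the significance rule. Section 9.1 aims at change through time, and the rule hardly touches that contrast (step 8). This is correct: the saving comes from how baseline BFI is used, and the rule is faulted because it leaves the model unfixed.

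The range also depends on assumptions. The 25% end follows from the ICC in section 9.2, with no truncation and a known slope. The 10% end needs assumed baseline means and truncation of the baseline score itself. Sections 4.7.1 and 4.7.2 fit step 5 better, where the saving against change is 25–28%, at or just above the top of the range.

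Participants with baseline only add nothing to the arm contrast under equal baseline means: the variance is 0.400 with or without them. Keeping them serves the all-available-data principle of section 9.1.2, not precision.

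The equal-means constraint needs BFI recorded before allocation is disclosed. Section 4.7.2 combines randomisation and baseline in one visit. It lists the questionnaires before acupressure instruction but does not say when allocation is revealed. The constraint is reasonable on that condition, which should be written in.

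Finally, this is an exploratory pilot that names no week-6 primary contrast, and the planned model is valid. That limits the severity. It does not remove the point, since at ICC 0.5 without truncation the saving is the same for the raw and the change contrast, and the remedy needs no new data.

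**Conclusion.** The concern holds. The covariate set is data-driven, the screening test is not defined for four arms, and baseline BFI is used inefficiently. The saving in week-6 contrast variance is 22–25% at the plan's ICC of 0.5 without truncation, and about 9–20% if the entry rule truncates the baseline score (assumed means 4 to 7). If the rule acts on the screening score, it is 15–21% against the raw difference or 25–28% against change. The 2-point contrast gains about 0.03 to 0.11 in power, depending on the case; 1-point contrasts stay underpowered. No bias or type I error inflation is claimed. The change should be made, but the trial's validity does not depend on it.

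**What to change.** 1. In section 9.1, delete the rule that adjusts for variables significantly different at baseline. In section 9.0, describe baseline characteristics by arm without tests.

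2. Pre-specify one model for BFI and each secondary outcome:
   - **Preferred:** a mixed model with all visits as responses and baseline means constrained equal across arms. It keeps every participant with a baseline value, in line with section 9.1.2.
   - **Alternative:** post-baseline visits as responses (weeks 2, 6 and 10 for BFI; weeks 6 and 10 for BPI, PSQI and SF-36), with the baseline value of that outcome as covariate. This costs one degree of freedom and about 1.9% of variance, and drops participants with no post-baseline value.

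3. Do not simply add baseline BFI to the planned model while week 0 stays a response. In 40 simulated data sets the visit-by-group estimate and its standard error (mean 0.728) were unchanged, a saving of 0%.

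4. State in section 4.7.2 that baseline questionnaires are completed before allocation is disclosed.

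5. Name any further prognostic covariates in advance (baseline SLAQ, for example) and include them whatever their balance.

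The cost is a wording amendment, with IRBMED approval under section 8.3.1. No visits, data or patients are added. The gain for BPI, PSQI and SF-36 is unknown, because the documents give no correlation for them.
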